QoL component grid. True Positive (TP), False Positive (FP), True Negative (TN) and False Negative (FN) will be defined using a contingency table. These quantitative variables will be used to calculate the sensitivity (proportion of actual satisfied patients that are correctly identified as such) and specificity (proportion of actual unsatisfied patients that are correctly identified as such) of the PSO-TARGET QoL Component grid, compared to the quality of life given by the DLQI. If these metrics reach a certain threshold (85%), the PSO-TARGET QoL component grid will be considered for additional studies in order to validate it at a larger scale and further demonstrate it is as much sound in assessing the patients' quality of life as the DLQI.

Because of the fact that alexithymia is highly prevalent in psoriasis patients, the grid will be administered to the patient after he/she had spontaneously expressed his/her treatment expectations. This should help the patient to narrow down the specific goal where his/her expectation belongs. In addition, as part of a secondary objective the treating physician will also choose an item from the table based on what he/she perceives in terms of patient's expectations without disclosing it to the patient. This will allow us to evaluate the level of accordance between the physician-chosen and the patient-chosen therapeutic goal. As another secondary endpoint, the level of achievement of the therapeutic goal will be assessed at 12/16 weeks and followed-up for 52 ± 4 weeks. Patients scoring the treatment as "satisfied or very satisfied" will be considered as having achieved their therapeutic goal. Another endpoint of interest (secondary) will be to assess, after 12/16 weeks of treatment, if the patient chooses a new therapeutic goal, different from the one he initially defined.

It is important to note that, this study being observational, none of the visits (baseline and follow-ups) are specific to the trial but part of the dermatologists' standard of care in both countries (France and Belgium). In addition, in order to limit variability in terms of treatment profiles (dosage and administration schedule) and thus to keep the study population as homogenous as possible, it has been decided to include only patients treated by Kyntheum®, in other terms Kyntheum® treatment is an accessory to the study but PSO-TARGET will not assess Kyntheum® efficacy *per se*.

The study objectives are the following:

Primary objective:

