THIS DOCUMENT CONTAINS TRADE SECRETS, AND/OR COMMERCIAL OR FINANCIAL INFORMATION, PRIVILEGED OR CONFIDENTIAL, DELIVERED IN CONFIDENCE AND RELIANCE THAT SUCH INFORMATION WILL NOT BE COPIED OR MADE AVAILABLE TO ANY THIRD PARTY WITHOUT THE WRITTEN CONSENT OF LEO PHARMA A/S

- ✓ Sensitivity : 90%
- ✓ Absolute precision : 10%
- ✓ Type I error : 5%
- ✓ Power at 80%
- ✓ Prevalence: 80% (estimated rate of patients with a DLQI 0-1 after 12 weeks of treatment.

Based on these hypotheses, the sample size needed is estimated at 134 evaluable patients.

Assuming 10% of patients will not be evaluable on main criterion, **150 patients have to be included.**

Data analysis

Analysis of the primary endpoint

The performance of the PSO-TARGET QoL component grid to assess the treatment impact on the patients' quality of life will be determined by calculating the sensitivity and specificity of the grid compared to the DLQI (reference). The grid will be validated if both the specificity and sensitivity parameters reach the 85% threshold.

Milestones

Regulatory Submissions: Q2 2020

Start of data collection Q3 2020

End of data collection Q2 2022

Final report Q4 2022

5 Amendments and Updates

None

THIS DOCUMENT CONTAINS TRADE SECRETS, AND/OR COMMERCIAL OR FINANCIAL INFORMATION, PRIVILEGED OR CONFIDENTIAL, DELIVERED IN CONFIDENCE AND RELIANCE THAT SUCH INFORMATION WILL NOT BE COPIED OR MADE AVAILABLE TO ANY THIRD PARTY WITHOUT THE WRITTEN CONSENT OF LEO PHARMA A/S

6 Milestones

Planned dates for study milestones are indicated in the table below:

Milestone	Planned Date
Start of data collection	Q3 2020
End of data collection	Q2 2022
Final study report	Q4 2022

The start of the study is defined as the date on which the first information on a study patient is recorded in the study dataset. LEO will ensure that End-of-Data Collection (End of Study) notification is submitted to the concerned authorities and IECs for each site, for each country and for the complete study.

Based on upcoming knowledge, LEO might choose to terminate the study prematurely. In such case the Committee(s), study sites, IECs and authorities will be informed promptly.

7 Rationale and Background

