
level of concordance of this satisfaction level and the overall quality of life as defined by the DLQI at the same time point. It is important to consider that systemic treatment by Kyntheum® is an accessory to the study but the objective of the PSO-TARGET is not to evaluate Kyntheum® efficacy.

As part of secondary objectives, in parallel to that initial assessment by the patient, the physician will tick on the grid what would be his patients therapeutic goal based on what he knows/understands from the patient's disease history and therapeutic desires. At the time of his/her assessment, the physician will be blinded of the patient's choice of therapeutic goal. The accordance between the physician-chosen and the patient-chosen dimensions will be analyzed. The 12 items of the tool will be pooled and analysed by component (physical, subjective, relational and therapeutic). At 52 weeks, among other secondary endpoints, the maintenance of the level of achievement of the initial objective observed at the 1st follow-up visit, will be assessed.

One of the innovative aspects of this exploratory observational study will be the administration of a psoriasis-specific quality of life component grid containing 12 treatment objectives grouped in the 4 quality of life components/dimensions usually impacted in patients suffering from chronic diseases (Chassany, 2003; Forestier et al., 2019). Those dimensions accounting for the burden to bear when suffering from a chronic disease are the following: Physical, Subjective, Relational/Social and Therapeutic. Each dimension will include 3 patient's therapeutic goal based on dermatologists' clinical experience and reviewed by an expert on psychometric tools.

This is an exploratory study, a first step to assess the interest of the PSO-TARGET component grid. If the sensitivity and specificity reach an acceptable threshold (85%), the potential of the PSO-TARGET grid will be considered for validation in larger clinical studies. Indeed, more studies will be needed to test other attributes in order to fully validate the PSO-TARGET grid as an alternative to the DLQI for QoL assessment. Once the PSO-TARGET component grid is validated, it will prove to be a useful tool for a better design of a therapeutic objective from the physician and thus a better care brought to the patient which should improve the patient's satisfaction and treatment adherence.

8 Research Question and Objectives

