9.5 Study Size

The main criterion is the sensitivity of the PSO-TARGET tool (percentage of patients who consider their target objective as being achieved after 12/16 weeks of treatment as defined by a "satisfied or very satisfied" response, assessed on a 4 points Likert scale, among patients with a DLQI total score of 0 or 1).

The sample size calculation is based on the following hypotheses:

Sensitivity: 90%

Absolute precision : 10%

Type I error : 5%

Power at 80%

Prevalence: 80% (estimated rate of patient with a DLQI 0-1 after 12 weeks of treatment)

Hypothesis :

THIS DOCUMENT CONTAINS TRADE SECRETS, AND/OR COMMERCIAL OR FINANCIAL INFORMATION, PRIVILEGED OR CONFIDENTIAL, DELIVERED IN CONFIDENCE AND RELIANCE THAT SUCH INFORMATION WILL NOT BE COPIED OR MADE AVAILABLE TO ANY THIRD PARTY WITHOUT THE WRITTEN CONSENT OF LEO PHARMA A/S

$H_0 : Se = Se_0$

$H_1 : Se = Se_1 > Se_0$

With Se =sensitivity, $Se_0=0.8$ and $Se_1=0.9$

Using the binomial probability formula, the sample size necessary to meet both a significance level and a power requirement may be found by solving the following two equations simultaneously :

Significance level $B(s_1 > s \alpha | n_1, Se_0) = \alpha$

$B(s_1 > s \alpha | n_1, Se_1) = 1 - \beta$

Where n_1 : patients with a DLQI 0-1, s_1 : patients with a DLQI 0-1 and a positive test outcome

With $\alpha=0.05$ and $1 - \beta=0.8$

To obtain n , n_1 is inflated by the prevalence P (rate of patients with a DLQI 0-1 = 80%), to obtain $n = n_1 / P$

The software used is PASS version 12, using the Li and Fine method (Li and Fine, 2004).

Based on these hypotheses, the sample size needed is estimated at 134 evaluable patients.

Assuming 10% of patients will not be evaluable on main criterion, **150 patients have to be included.**

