9.8 Statistical Analysis Plan

Data analyses will be performed using SAS Version 9.4 or further (SAS Institute, Cary, NC USA software).

Quantitative parameters will be described using the following summary descriptive statistics: number of non-missing values, mean, standard deviation, median, first and third quartiles, and minimum and maximum values.

Qualitative parameters will be described overall using frequencies and percentages. Percentages will be calculated on the number of non-missing observations.

The level of significance for all comparisons is set at 0.05 using two-tailed tests. Confidence intervals at 95% could be provided, if relevant.

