9.8.3 Sensitivity/sensibility analysis

- Analysis of the primary endpoint

The primary endpoint will be the evaluation at week 12/16 of the sensitivity and the specificity, compared to the DLQI as a standard, of the PSO-TARGET QoL component grid to assess the level of satisfaction of patient achieving the therapeutic goal, identified by himself.

The therapeutic objective will be considered as achieved if the patient gives the responses “Satisfied” or “Very Satisfied” on the Likert scale. The response will then be compared to the DLQI score at 12/16 weeks.

It will be described on the efficacy population.

A contingency table will be constructed as follows:

PSO-TARGET \ DLQI	0-1	2-5	6-10	11-20	21-30
Very satisfied	TP	FP	FP	FP	FP
Satisfied	TP	FP	FP	FP	FP
Unsatisfied	FN	TN	TN	TN	TN
Very unsatisfied	FN	TN	TN	TN	TN

This table can be summarized as :

PSO-TARGET \ DLQI	0-1	≥ 2
Very satisfied ou Satisfied	TP	FP
Unsatisfied ou Very unsatisfied	FN	TN

TP: True positive

FP: False Positive

FN: False Negative

TN: True Negative

The validity of the QoL component grid will then be assessed by calculating the following parameters:

Sensitivity: defined as the probability to have patients who have reached their therapeutic target (who have responded « satisfied » or « very satisfied » on the Likert scale, globally and in each major domains) among patients with a DLQI score between 0 and 1.

In other terms the sensitivity is defined as the **concordance** of the QoL component grid and the DLQI **for the patients with optimal quality of life**.

The sensitivity is calculated by:

$$Se = \frac{TP}{TP + FN}$$

Specificity: defined as the probability to have patients who have not reached their therapeutic target (who have responded « unsatisfied » or « very unsatisfied » on the Likert scale, globally and in each major domains) among patients with a DLQI score ≥2.

In other terms the specificity is defined as the **concordance** of the QoL component grid and the DLQI **for the patients with suboptimal quality of life**.

The specificity is calculated by:

$$Sp = \frac{TN}{FP + TN}$$

The QoL component grid will be validated if these two parameters reach the threshold of 85%.

THIS DOCUMENT CONTAINS TRADE SECRETS, AND/OR COMMERCIAL OR FINANCIAL INFORMATION, PRIVILEGED OR CONFIDENTIAL, DELIVERED IN CONFIDENCE AND RELIANCE THAT SUCH INFORMATION WILL NOT BE COPIED OR MADE AVAILABLE TO ANY THIRD PARTY WITHOUT THE WRITTEN CONSENT OF LEO PHARMA A/S

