Objective	Statistical analysis	Exposure measure	Outcome measure	Covariates
1	Contingency table; Sensitivity / Specificity	N/A	Concordance level between PSO- TARGET Component grid and DLQI at 12/16 weeks	N/A

- Analysis of the secondary performance endpoints

Analyses of secondary endpoints will be performed on the efficacy population.

No replacement of missing data will be performed.

The same analysis as the primary performance analysis will be performed at 52 weeks.

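### The rule that declares the grid validated (observed sensitivity and specificity both at least 85%) is not the test that sized the study, so alpha 5% and power 80% do not describe the decision

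*Protocol*

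**What the plan says.** **Sizing (section 9.5, repeated in the section 4 abstract).** The protocol writes "The main criterion is the sensitivity of the PSO-TARGET tool". The null is Se0 = 0.80 and the alternative Se1 = 0.90, with alpha 0.05 and power 0.80. The prevalence of DLQI 0-1 is taken as 80%. The result is 134 evaluable patients and 150 included. No hypothesis, error rate or sample size is given for specificity.

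**Decision (section 9.8.3).** "The QoL component grid will be validated if these two parameters reach the threshold of 85" per cent. The abstract (section 4, Data analysis) repeats it: "The grid will be validated if both the specificity and sensitivity parameters reach the 85% threshold".

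**Analysis.** For the primary objective, the summary table in section 9.8.3 lists "Contingency table; Sensitivity / Specificity". The general rule in section 9.8 is "The level of significance for all comparisons is set at 0.05 using two-tailed tests"; 95% confidence intervals are optional there.

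**Meaning of reaching 85%.** Elsewhere the consequence is weaker. In the section 4 rationale the grid "will be considered for additional studies in order to validate it at a larger scale", and in section 7 "the potential of the PSO-TARGET grid will be considered for validation in larger clinical studies".

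**The concern.** The protocol contains two different criteria. One is a hypothesis test on sensitivity with null value 0.80, which produced the sample size. The other is a pair of point-estimate cut-offs at 0.85, which produces the conclusion. The decision rule does not mention 0.80, a test or a confidence bound, and it adds a second parameter that was never sized.

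A reader who sees alpha 5% and power 80% in the study-size section will naturally take them as properties of the study's one primary conclusion, and they are not. An observed sensitivity of 85.0% to 86.9% could be reported as validation although its two-sided exact 95% interval does not exclude the null the study was sized to reject. The word used for success is also stronger in two places than in the two others that describe the same result.

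**Working it through.** **Inputs.** Se0 = 0.80, Se1 = 0.90, alpha 0.05, power 0.80, prevalence 0.80, N = 134 (section 9.5); two-tailed testing (section 9.8); 85% for both parameters (sections 4 and 9.8.3). Sensitivity and specificity come from different patients, so their counts are independent given the split. The protocol assumes no value for specificity, so a range is shown.

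**1. Reproduce the plan's 134.** Find the smallest n1 with P(X ≥ c | n1, 0.80) ≤ 0.025 (upper tail of a two-sided 5% test) and P(X ≥ c | n1, 0.90) ≥ 0.80.

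- Result: n1 = 107, c = 94, size 0.0233, power 0.819.
- 107 / 0.80 = 133.75, which rounds up to 134. The stated figure is reproduced.
- With an upper tail of 0.05, the smallest n1 is 82 and N = 103, which does not reproduce it. At n1 = 107 the one-sided 5% critical value would be 93 (size 0.043).

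The expected split is 107 with DLQI 0-1 and 134 − 107 = 27 with DLQI ≥ 2.

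**2. Pass marks of the 85% rule.**

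- Sensitivity: 0.85 × 107 = 90.95, so 91/107.
- Specificity: 0.85 × 27 = 22.95, so 23/27.

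Sensitivity counts of 91 to 93 pass the rule without rejecting 0.80 on the two-sided reading; 91 and 92 do so on the one-sided reading.

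| Count | Estimate | Exact 95% CI |
|---|---|---|
| 91/107 | 85.0% | 76.9% to 91.2% |
| 93/107 | 86.9% | 79.0% to 92.7% |
| 94/107 | 87.9% | 80.1% to 93.4% |
| 23/27 (specificity) | 85.2% | 66.3% to 95.8% |

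**3. Each half alone.**

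- Sensitivity: P(X ≥ 91 | 107, 0.80) = 0.116 and P(X ≥ 91 | 107, 0.90) = 0.963.
- Specificity: P(X ≥ 23 | 27, Sp) = 0.158, 0.348, 0.619 and 0.873 at Sp = 0.75, 0.80, 0.85 and 0.90.

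**4. Both halves.** P(declared validated) = P(X ≥ 91 | 107, Se) × P(Y ≥ 23 | 27, Sp). The averaged column lets the number with DLQI 0-1 vary as Binomial(134, 0.8).

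| True Se | True Sp | Split 107/27 | Averaged |
|---|---|---|---|
| 0.80 | 0.75 | 1.8% | 1.1% |
| 0.80 | 0.80 | 4.0% | 2.6% |
| 0.80 | 0.85 | 7.2% | 5.1% |
| 0.80 | 0.90 | 10.1% | 7.8% |
| 0.80 | towards 1 | 11.6% | 9.6% |
| 0.90 | 0.80 | 33.5% | 26.3% |
| 0.90 | 0.85 | 59.6% | 50.5% |
| 0.90 | 0.90 | 84.1% | 77.3% |

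At Se = 0.80 and the 107/27 split, the probability passes 2.5% at Sp of about 0.77 and 5% at Sp of about 0.82. At the planned Se = 0.90, it depends almost entirely on a specificity the plan never states.

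**The case against.** The protocol ties alpha and power to sensitivity only and claims no error rate for the 85% rule, so a reader's confusion is an inference. The study calls itself exploratory and a first step, and a point-estimate go/no-go screen is a common choice at that stage. The joint rule gives 4.0% at Se = Sp = 0.80 and 84.1% at 0.90/0.90, close to 5% and 80%. Averaged over the split, the 5% level is passed only when true specificity is about 0.85 or more. A statistical analysis plan that is not at hand may add intervals or a test.

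Much of this limits the weight of the point without removing it. The exploratory status does reduce the consequence. The closeness to 5% and 80% is a coincidence of combining two criteria: with sensitivity at the null and specificity at 0.90 the rate is 10.1%. The decision rule is fixed in the protocol, in two places, so it is not a detail left for later. Missing intervals alone would be no fault; a fixed rule that bypasses the sized test is.

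Two further objections stand. The weaker half is specificity, which passes 34.8% of the time at a true value of 0.80. Tightening sensitivity alone hardly changes that: at Se = 0.90 and Sp = 0.80 the joint pass probability would go from 33.5% to 0.819 × 0.348 = 28.5%. Also, 93/107 does reject on a one-sided 5% reading, so the 85.0% to 86.9% range applies to the two-sided interval; on the one-sided reading it ends at 92/107 (86.0%).

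**Conclusion.** The concern holds. The sample size is arithmetically right for the test in section 9.5, but that test does not decide anything. The rule that does decide has no stated operating characteristics. Its chance of a positive declaration at the null sensitivity ranges from 1.8% to 11.6% as specificity goes from 0.75 towards 1 (107/27 split), against a nominal 5%. Its chance of success at the planned sensitivity of 0.90 ranges from 33.5% to 84.1% for specificity 0.80 to 0.90, against a nominal 80%.

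These figures assume 134 evaluable patients, 80% with DLQI 0-1, and the specificity values shown, which are this review's assumptions because the protocol gives none. The point should be fixed, but it is not fatal: the study is exploratory and further studies are foreseen.

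**What to change.** Choose one of two options, in sections 4, 9.5 and 9.8.3.

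- **Option A: link the decision to the sized test.** Require for sensitivity that the lower limit of the exact two-sided 95% confidence interval exceeds 0.80 (at least 94/107 at the planned size). Keep specificity of at least 85% openly as a point-estimate criterion, report its exact 95% interval, and claim no error rate or power for it. State in 9.5 that the power applies to sensitivity alone: 81.9% at n1 = 107, or 78.3% averaged over the split. The joint rule has 0.819 × 0.873 = 71.5% at Se = Sp = 0.90, or 63.6% averaged. The cost is a stricter sensitivity pass mark (87.9% rather than 85%) and a lower stated joint power, with the specificity error nearly unchanged.
- **Option B: keep 85% for both.** State the operating characteristics tabulated above, including 84.1% (77.3% averaged) at Se = Sp = 0.90, and stop presenting alpha 5% and power 80% as properties of the decision. The cost is giving up the claim of a controlled 5% error. This is the simpler route and suits an exploratory study.

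Under either option, replace the statement that the grid will be validated with the wording already used in the section 4 rationale and section 7, that it will be considered for validation in further studies. No extra patients or data are needed.

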The aim of this study is to evaluate, compared to the DLQI as a standard tool, the sensitivity and specificity of the PSO-TARGET QoL Component grid as a new QoL questionnaire for assessing the level of satisfaction of the psoriasis patients in achieving the therapeutic goal, identified by himself, after a biologic treatment. This study is the first step of an evaluation process aiming to validate the PSO-TARGET QoL Component grid. Ultimately, this tool will be used by physicians to devise a “Treat to patient satisfaction target” strategy that better suits their patients’ expectations. To construct this new questionnaire, the first step has been to collect psoriasis patients’ feedback on what is the aspect of their life that is the most impacted by the disease and which is the one they would want to improve the most. To this aim a retrospective survey based on the recollection and experience from 3 clinical dermatologists (2 French and 1 Belgian) of patient’s expectations, was conducted. The results of the survey have been used to generate a table containing 12 treatment goals equally distributed into the 4 major components classically used in quality of life studies in patients suffering from chronic diseases (physical, subjective, relational/social and therapeutic) (Chassany, 2003; Forestier et al., 2019). The proposed verbatim was then reviewed by a psychologist to ensure that there was a balance between the proposals; i.e. the vocabulary used was neutral enough not to guide the choices. This component grid will be administered to the patients prior to the initiation of a systemic treatment (Kyntheum® / brodalumab) to set up the main therapeutic objective (1 out of 12) fitting with his priority expectation from the upcoming treatment. The patient will only have access to the 12 treatment goals but not to the category headings. Because of the fact that alexithymia is highly prevalent in psoriasis patients, the grid will be submitted to the patient after he/she had been asked by the physician to express spontaneously his/her treatment expectations. This should help the patient to narrow down the item where his/her expectation belongs. At the 1st follow-up visit (12/16 weeks), the level of achievement will be assessed using a 4 points Likert scale (“very satisfied”, “satisfied”, “unsatisfied”, “very unsatisfied”). In order to evaluate the sensitivity and the specificity of the PSO-TARGET QoL component grid, the primary objective of the study will be to estimate the

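### The same primary result, sensitivity and specificity reaching 85%, makes the grid validated in two places and only a candidate for validation in larger studies in two others

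*Protocol*

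**What the plan says.** The primary analysis compares satisfaction on the PSO-TARGET grid at week 12/16 with the DLQI (0–1 against 2 or more), and gives a sensitivity and a specificity. The protocol states what follows from reaching 85% in four places.

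- Section 9.8.3: "The QoL component grid will be validated if these two parameters reach the threshold of 85" per cent.
- Section 4 (Abstract), Data analysis: "The grid will be validated if both the specificity and sensitivity parameters reach the 85% threshold".
- Section 4 (Abstract), Research question and objectives, on reaching the 85% threshold: "the PSO-TARGET QoL component grid will be considered for additional studies in order to validate it at a larger scale".
- Section 7, on reaching the same threshold: "the potential of the PSO-TARGET grid will be considered for validation in larger clinical studies". The next sentence adds that "more studies will be needed to test other attributes in order to fully validate the PSO-TARGET grid as an alternative to the DLQI".

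Section 7 also describes the stage of the work: "This study is the first step of an evaluation process aiming to validate the PSO-TARGET QoL Component grid".

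**The concern.** A decision rule needs one condition and one consequence. Here the condition is the same in all four places, but the consequence differs. In two places a pass completes validation; in the other two it opens the way to validation studies. The abstract disagrees with itself, and the rationale disagrees with the analysis section.

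At stake is the main conclusion of the study. Someone writing the report, or an SAP, would look to section 9.8.3 for the rule and would be entitled to report a validated instrument. Someone who relies on section 7 would report a grid worth testing further. If the choice stays open until the results are known, the more favourable wording can be picked afterwards.

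**Working it through.** **Step 1. Is it current text?** Section 5 lists no amendments, so all four statements are in force and none is superseded.

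**Step 2. Side by side.**

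| Place | Condition | Consequence |
|---|---|---|
| Abstract, Data analysis | sensitivity and specificity reach 85% | validated |
| Section 9.8.3 | the same | validated |
| Abstract, Research question and objectives | the same | considered for further studies whose purpose is to validate it |
| Section 7 | the same | considered for validation in larger studies; more studies needed for full validation |

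The count is two against two on an identical condition.

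**Step 3. Does any text reconcile them?** One would need a sentence saying that *validated* in section 9.8.3 means only that this study's criterion was met. There is none. Section 7 points the other way: it places validation after this study, and it speaks of the grid's usefulness to physicians as something that comes once validation is done.

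**Step 4. Which consequence fits the rest of the protocol?** The abstract and section 7 call the study exploratory, section 7 calls it a first step, and section 9.4 says the grid has never been used before. These agree with the limited consequence.

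**Step 5. Numbers, for context only.** The plan's own figure reproduces. An exact binomial test of sensitivity 0.80 against 0.90 (section 9.5), with 0.025 in the upper tail (two-tailed 0.05, section 9.8), needs 107 patients with DLQI 0–1. It rejects at 94 or more, with exact upper-tail error 0.0233 and power 0.819. At 80% prevalence, 107 / 0.80 = 133.75, which rounds up to the stated 134. The sample size is not in dispute.

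Of 134 evaluable patients, 134 × 0.80 ≈ 107 would have DLQI 0–1 and 134 − 107 = 27 would have DLQI 2 or more. Assume that reaching 85% refers to the point estimate (the protocol does not say) and that prevalence is 80%. The smallest passing counts are then:

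- sensitivity: 0.85 × 107 = 90.95, so 91/107 = 85.0%, exact 95% CI 76.9% to 91.2%;
- specificity: 0.85 × 27 = 22.95, so 23/27 = 85.2%, exact 95% CI 66.3% to 95.8%.

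These intervals would be the same if all four statements agreed, so they do not measure the contradiction. They only show how much a bare pass would leave uncertain.

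**The case against.** The strongest reply is that the four statements can be read together. Section 9.8.3 introduces sensitivity and specificity as the means of assessing the grid's validity, so *validated* at the end of that passage could mean only that these two parameters passed. The research-question text speaks of validating at a larger scale and of a further demonstration, and section 7 of validating fully; such graded wording leaves room for a first, study-level validation here. No text ranks section 9.8.3 above section 7, and a reader of the whole protocol meets the exploratory label repeatedly.

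This shows that the conflict may be loose drafting and that the sponsor probably intends the limited consequence. It does not remove the conflict. The limited meaning is never written, and section 7 attaches to the same threshold consideration *for* validation, which is hard to square with validation having been achieved.

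The objection does rule out several stronger readings that a reader might infer:

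- **That a pass leads directly to clinical use.** The abstract makes use by physicians conditional on validation, and section 7 presents it as the ultimate aim of a longer process. Immediate use is not stated.
- **That the grid is checked against a single reference and nothing else.** Satisfaction is also compared with PASI 90 (section 9.8.5), and the sensitivity and specificity analysis is repeated at 52 weeks (section 9.8.3).
- **That the confidence intervals give the size of this defect.** They describe precision under an assumed point-estimate rule, which is a separate matter.
- **That the study can support no validation claim of any kind.** Section 7 says only that full validation as an alternative to the DLQI needs more studies.

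**Conclusion.** The concern holds as an internal contradiction in the conclusion drawn from the primary endpoint. Two statements declare the grid validated at 85%, and two make it a candidate for validation at the same 85%. Following section 9.8.3 as written would yield a claim that section 7 reserves for later studies.

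The defect has no numerical size: endpoint, threshold, population, analysis and the 134 evaluable patients are the same under either wording. It is still worth correcting before results are seen, because it decides what the study may claim. The verdict rests on the text alone and needs none of the assumptions behind the context figures.

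**What to change.** In section 9.8.3 and in the abstract's Data analysis, replace the statement that the grid will be validated with the consequence section 7 already gives for reaching 85%: "the potential of the PSO-TARGET grid will be considered for validation in larger clinical studies". In both places add, as section 7 does, that full validation as an alternative to the DLQI needs further studies. All four statements then carry one consequence.

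The cost is a change to two sentences and a less favourable stated conclusion. Data collection, analysis and sample size are unaffected.
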